1.0 PROTOCOL SUMMARY AND/OR SCHEMA

This is a randomized phase II study that will test two different adjuvant temozolomide regimens in patients with newly diagnosed glioblastoma multiforme. The goal of this study is to identify a regimen that would be appropriate to bring to a phase III trial and compare to the standard dosing regimen of temozolomide recently reported by Stupp et al. in the New England Journal of Medicine. Secondary goals of this study include: prospective analysis of the prognostic impact of MGMT status and generation of preliminary data regarding this treatment strategy for other types of malignant glioma.

```
Focal RT 6000 cGy/ Temozolomide 75 mg/m^2
```

2.0 OBJECTIVES AND SCIENTIFIC AIMS

Primary objective: To determine the overall survival of patients with newly diagnosed glioblastoma multiforme treated with concurrent temozolomide and radiotherapy followed by dose dense or metronomic dosing of temozolomide and maintenance cisretinoic acid.

Secondary objectives:

- 1. Progression free survival
- 2. To evaluate the prognostic impact of methylated MGMT status.
- 3. To collect preliminary data on the efficacy of this regimen and impact of MGMT status in other malignant glioma subtypes.

3.0 BACKGROUND AND RATIONALE

3.1 Background

The treatment of recurrent malignant gliomas represents a therapeutic challenge. Even with maximum treatment at initial diagnosis, malignant gliomas have a dismal prognosis. Standard management is optimal surgical resection followed by involved field radiotherapy. Historically, the role of chemotherapy has been controversial since median survival is not improved although a minority of patients may have prolonged survival. A randomized clinical trial failed to show any benefit (Medical research council brain tumor working party, 2001), but a prior meta-analysis of published randomized trials demonstrated a modest survival benefit for patients receiving adjuvant chemotherapy following radiotherapy (Fine et al., 1993).

Temozolomide is a relatively new oral alkylating agent that was developed for the treatment of malignant glioma. Initially approved in the United States for the treatment of recurrent anaplastic astrocytoma, temozolomide has been observed to have activity in the adjuvant treatment of glioblastoma multiforme.^{1,2} Furthermore, preclinical studies demonstrated evidence of synergistic activity of temozolomide when given in conjunction with radiotherapy. The promising results of a phase II study of concomitant and adjuvant temozolomide and radiotherapy in newly diagnosed patients led to a large international phase III study to confirm these results.³ The primary endpoint of this phase III study was to compare overall survival in newly diagnosed glioblastoma multiforme patients treated with radiotherapy alone versus concomitant temozolomide and radiotherapy followed by adjuvant temozolomide. 573 patients with newly diagnosed GBM at 85 institutions were randomized to receive either radiotherapy alone (n = 286) or concomitant and adjuvant temozolomide (n=287). Patients were stratified on the basis of age, performance status, treating institution, and extent of resection. Patients treated with radiotherapy alone received 30 fractions of 200 cGy using standard conformal treatment planning. The schedule of temozolomide used during radiotherapy (concomitant dosing) was 75mg/m^2 daily including weekends (days when radiotherapy was not administered) for six weeks. Adjuvant therapy began four weeks after completion of radiotherapy with the standard recommended dose of temozolomide: $150-200 \text{ mg/m}^2/\text{day}$, days 1-5; a maximum of six cycles were administered.

IRB#: 05-079A(17)

With a median follow up for surviving patients of more than two years, there was a statistically and clinically significant improvement in median (14.6 v. 12.1 months) and two year overall survival (26 v. 10%) for patients treated with concomitant and adjuvant temozolomide as compared with radiotherapy alone. Median progression free survival was also significantly improved in the concomitant treatment group (p < 0.0001). Of importance, the two treatment groups were well balanced for known prognostic variables and the treatment was well tolerated in both groups with no unexpected toxicity observed. No cases of Pneumocystis carinii pneumonia were reported. Ten percent or less of those patients receiving temozolomide developed grade 3 or higher myelosuppression or fatigue. This was the first prospective phase III study to definitively show that chemotherapy has a clear role in the treatment of glioblastoma multiforme.⁷ Previously, there was significant evidence that chemotherapy played an important role in the treatment of glioblastoma multiforme⁴; however, the lack of level I evidence may have dissuaded conservative practitioners from pursuing aggressive therapy. While the overall prognosis remains poor even with the addition of concomitant and adjuvant temozolomide, a significant proportion of patients remain alive at two years.

A subset analysis of patients enrolled on the phase III trial found that benefit of concomitant and adjuvant temozolomide was maintained across most known prognostic variables. Those patients with a poor performance status, or whose tumors were only biopsied, derived less benefit. Subset analysis was also performed using the RTOG RPA classification⁵. Improvement in progression free survival was maintained in all relevant classes (classes III, IV, V). Class III and IV patients treated with concomitant and adjuvant therapy maintained the survival benefit. Correlative tissue analysis of patients enrolled suggests that patients whose tumors have a methylated form of an excision repair enzyme, O-6-methylguanine-DNA methyltransferase (MGMT), are particularly likely to benefit from concomitant and adjuvant temozolomide.^{6,8} Patients with methylated MGMT had approximately a 50% chance of surviving for two years. Methylation functionally inactivates the MGMT which in the active form is known to result in resistance to alkylating agents. This observation may be critical to the development of other successful therapeutic strategies to enhance chemosensitivity. MGMT analysis should be incorporated into prospective clinical trials of alkylating agents.

Experimentally and in vivo, temozolomide is schedule dependent.⁹ Recent studies in recurrent malignant gliomas used 150-200 mg/m²/daily for 5-days in a 28-day cycle.^{1,2} However, a phase-I study of low dose continuous temozolomide defined a maximum tolerated dose (MTD) at 75 mg/m²/day for 42-days in a 70-day cycle (Brock et al., 1998). This regimen provides 2.1 fold greater drug exposure over 4-weeks compared to the standard 200 mg/m² dose with comparable toxicity. There was no evidence of drug accumulation and furthermore, this extended schedule may deplete O(6)-alkyl guanine-DNA alkyl transferase (AGT) levels, a potential mechanism of drug resistance. This treatment schedule may have improved efficacy as a result of increased drug exposure and decreased drug resistance without having an increase in treatment related toxicity.

IRB#: 05-079A(17)

Other temozolomide schedules can also be used to increase the dose density or to deliver continuous drug without interruption, thereby exploiting successful chemotherapy dosing strategies used in other solid tumors.

3.2 Rationale for the proposed study

This study is an effort to build on the results of the recently presented EORTC/NCIC study demonstrating that concurrent temozolomide and radiotherapy followed by 6 months of adjuvant temozolomide can significantly extend the life and disease free survival of patients with glioblastoma multiforme. The proposed study will provide preliminary data regarding several important questions:

Is it feasible and effective to increase the delivered dose of adjuvant temozolomide (dose dense chemotherapy)?

The concept of dose dense chemotherapy was pioneered by [name] and others at MSKCC in an effort to improve outcomes of patients with metastatic and high risk breast cancer. In this model dose density (body size adjusted dose divided by unit time) seeks to improve the overall impact of therapy by decreasing the time between dosing intervals and thereby decreasing the regrowth of resistant tumor cells between cycles of chemotherapy. This model can be easily applied to glioma by utilizing one of the alternate dosing regimens for temozolomide that delivers 150mg/m² daily for 7 days on 7 days off. This schedule is well tolerated and effectively delivers more than twice the standard dosing regimen and decreases the interval between cycles from 23 days to 7 days.¹¹

Is it feasible and effective to deliver continuous low dose temozolomide without interruption (metronomic chemotherapy)?

Metronomic chemotherapy (antiangiogenic scheduling) has been proposed as an alternate dosing schedule for conventional chemotherapy. The theory is that the obligatory rest period in conventional chemotherapy permits the recovery of endothelial cells and that altering the dosing regimen to allow for continuous low dose exposure without myelosuppression and other dose limiting side effects will prevent the repair and recovery of tumor endothelium.¹²⁻¹⁵ Therefore we will plan to administer temozolomide at 50mg/m² daily without interruption to half of the patients enrolled on this trial and assess feasibility and efficacy. This schedule was chosen because it can be administered in a continuous fashion in patients with recurrent glioma for as long as 2 years (personal communication, [name], Toronto), all other schedules of temozolomide require interruption to recover from treatment related toxicity.

Is it possible to improve the outcome of patients with unmethylated or active MGMT by the use of alternate dosing regimens that effectively deplete MGMT levels?

IRB#: 05-079A(17)

An important mechanism of resistance to alkylating agents is the presence of active repair enzymes such as MGMT. In the study by Stupp et al. patients with methylated or inactive *MGMT* were retrospectively described as having the greatest benefit while patients with unmethylated or active *MGMT* had substantially less benefit from the addition of temozolomide. However, patients with active MGMT still had a statistically significant benefit in terms of progression free survival and 2 year overall survival with the addition of temozolomide. Both of the alternate dosing regimens that we will randomize patients to have been demonstrated to result in significant depletion of MGMT.¹⁶ Therefore, in theory either regimen may result in increased treatment sensitivity.

Does maintenance therapy help to maintain remission?

One of the down sides of administering a 6 month course of adjuvant therapy to patients with glioblastoma is the high risk of tumor recurrence. As a result many patients and clinicians are uncomfortable truncating therapy after 6 months in a patient who is doing well. There is some data to suggest that some sort of maintenance therapy may be effective and substantially less toxic than continuing myelos uppressive chemotherapy indefinitely. One such study found that high grade glioma patients with a complete remission treated with maintenance 13-cis retinoid acid maintained their remission for an average of 74 weeks after starting maintenance therapy.¹⁰ This promising result merits further prospective investigation.

Is the EORTC/NCIC regimen beneficial for patients with other types of high grade gliomas?

The definitive answer to the above question will require a prospective randomized trial. However, given the relative scarcity of these patients and numerous competing trials a prospective randomized trial may not be feasible. We would propose allowing patients with other malignant gliomas to enroll in our trial to obtain preliminary data. The sample size and statistical design/accrual goals will be built around the glioblastoma population, other tumor types would be accrued and reported descriptively as part of the whole and as a subset.

MGMT Correlative study:

We plan to prospectively assay available tissue for *MGMT* methylation status to see if our results correlate with disease control/patient outcome. If so, this would support the retrospective observation of the EORTC/NCIC.

4.0 OVERVIEW OF STUDY DESIGN/INTERVENTION

4.1 Design

This will be a single institution randomized phase II study that will allow us to concurrently assess the efficacy and toxicity of two different schedules of adjuvant temozolomide. The prospective analysis and stratification based on *MGMT* status will allow us to confirm the observation of the EORTC/NCIC study.

4.2 Intervention

The goal of this study is to look at two alternative ways to enhance chemotherapy delivery for patients with newly diagnosed malignant glioma. All patients will receive concurrent temozolomide and radiotherapy followed by one of 2 different adjuvant temozolomide regimens. They will be randomized to these adjuvant regimens on the basis of tumor histology and KPS. At the completion of 6 cycles all patients will receive maintenance cis-retinoic acid until tumor progression.

4.3 Statistics

A Simon mini-max two stage design will be used for each arm of the protocol. If either regimen shows a one year survival probability of 70% or greater (27 patients surviving at one year) then a phase III trial comparing this regimen to the regimen reported by Stupp et al. will be proposed.

5.0 THERAPEUTIC/DIAGNOSTIC AGENTS

Temozolomide is an oral cytotoxic alkylating agent which undergoes spontaneous conversion to MTIC, the active metabolite of dacarbazine, at physiologic pH. It has demonstrated activity against malignant glioma.

Temozolomide is manufactured by Schering Plough, Inc. It is available as 5, 20, 100 and 250 mg capsules. The 20mg and 100mg capsules are projected to be stable for at least 30 months when stored between 2 and 30C in amber glass bottles. The 5mg and 250mg capsules are projected to be stable for at least 12 months under the same conditions.

Commercially available drug supply will be used for this study.

Cis-retinoic acid is an oral retinoid that is manufactured by Roche Pharmaceuticals, Inc. and supplied as 10, 20 and 40mg capsules.

Commercially available drug will be used for this study.

6.0 CRITERIA FOR SUBJECT ELIGIBILITY

Any adult patient with a newly diagnosed malignant glioma with available tissue would be eligible to participate.

6.1 Subject Inclusion Criteria

- Pathologic evidence of a malignant glioma.
- Tissue block or unstained slides must be available for *MGMT* analysis.
- Age 18-70
- KPS > 50
- Granulocyte count >1.5 X $10^9/L$
- Platelet count >99 X $10^9/L$
- SGOT < 2.5X upper limit of normal (ULN).
- Serum creatinine < 2X ULN.
- Bilirubin < 2X ULN.
- All patients must sign written informed consent.

6.2 Subject Exclusion Criteria

- Any prior chemotherapy, radiotherapy and biologic therapy for glioma.
- Any prior experimental therapy for glioma.
- Other concurrent active malignancy (with the exception of cervical carcinoma in situ or basal cell ca of the skin).
- Serious medical or psychiatric illness that would in the opinion of the investigator would interfere with the prescribed treatment.
- Pregnant or breast feeding women.
- Refusal to use effective contraception.

7.0 RECRUITMENT PLAN

Recruitment Plan

Patients will be recruited from the Neurology and Neurosurgery clinics at Memorial Sloan Kettering Cancer Center. All patients will be seen by a Neuro-oncology attending. All patients enrolled on the trial must sign written informed consent. There are no gender or racial restrictions.

8.0 PRETREATMENT EVALUATION

The following studies are required within two weeks prior to starting concurrent chemotherapy and radiotherapy:

• Complete history and physical exam including neurologic exam.

IRB#: 05-079A(17)

- Height and weight.
- CBC including WBC differential and platelet count.
- Comprehensive chemistry panel.
- Contrast enhanced MRI scan of the Brain* (this scan should ideally be performed within 72 hours of surgery and does not need to be repeated within the two weeks prior to treatment onset)

9.0 TREATMENT/INTERVENTION PLAN

9.1 Concurrent temozolomide and radiotherapy

This treatment should start within 6 weeks of surgical resection.

Standard focal external beam radiotherapy will be delivered using conventional radiation planning (3D conformal). The total dose should be approximately 6000 cGy (+/- 5%). Stereotactic boost is not allowed. Patients may receive their radiotherapy at MSKCC or locally provided that treatment planning and summary is available.

Temozolomide will be given at a dose of 75mg/m2 daily for the complete course of radiotherapy. Patients will start temozolomide the night before they receive the first dose of radiotherapy and take the last dose on the final day of radiotherapy. Patients will dose on weekends and holidays when radiotherapy is not scheduled. Supportive anti emetic therapy will be prescribed per institutional guidelines or at the discretion of the treating physician.

9.2 Randomized adjuvant therapy

This therapy will begin 2- 4 weeks after the completion of radiotherapy and will last for a total of 6 cycles (1 cycle = 28 days). Patients will be randomized to receive dose dense or metronomic temozolomide on the basis of histology and KPS.

9.21 Dose dense temozolomide

Temozolomide 150 mg/m^2 will be given to patients on days 1-7 and 15-21 of each 28 day cycle. Supportive anti-emetic therapy will be prescribed per institutional guidelines or at the discretion of the treating physician. Growth factors may be used to treat low blood counts but may not be given prophylactically.

9.22 Metronomic temozolomide

Temozolomide 50mg/m² will be given to patients on days 1-28 of each 28 day cycle. Supportive anti-emetic therapy will be prescribed per institutional guidelines or at the discretion of the treating physician. Growth factors may be used to treat low blood counts but may not be given prophylactically.

9.3 Maintenance cis-retinoic acid.

This therapy will start at the completion of 6 cycles of adjuvant temozolomide in all patients who have had no clinical or radiographic evidence of tumor progression. Treatment will continue in 28 day cycles until tumor progression.

13-cis retinoic acid 100 mg/m^2 will be given on days 1-21 of each 28 day cycle. (Minor variations in dose are allowed given limited pill strength options). On the first cycle patients may be given a titrated dose to evaluate tolerability.

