10.0 EVALUATION DURING TREATMENT/INTERVENTION

During concurrent temozolomide and radiotherapy:

- CBC every week.
- Brief physical exam weekly by radiation oncology.
- Contrast enhanced MRI (including perfusion) at the completion of radiotherapy and prior to initiation of adjuvant therapy – this will be considered a new baseline MRI and all patients may continue to adjuvant temozolomide.

During adjuvant temozolomide:

- CBC every week
- Monthly exam
- Contrast enhanced MRI (including perfusion) after every 2 cycles of therapy patients with evidence of tumor progression as compared to the post radiotherapy MRI will be removed from the study.
- Monthly comprehensive chemistry panel.

During maintenance cis-retinoic acid:

- Approximately monthly exam for 6 months then approximately every 2-3 months thereafter.
- Monthly CBC, comprehensive chemistry panel and lipid panel.
- Contrast enhanced MRI (including perfusion) after every 2-3 cycles of therapy patients with evidence of tumor progression as compared to the post radiotherapy MRI will be removed from the study.

IRB#: 05-079 A(17)

MGMT analysis:

Unless MGMT analysis was already performed as part of routine care at MSKCC or an MSKCC designated laboratory, *MGMT* methylation analysis will be performed by real-time PCR using TaqMan machine via OncoMethylome Sciences SA. Ten paraffin slides (around 10 micron), heated or baked (maybe less than 65C) per patient will be required. DNA will then be isolated and modified for real-time PCR on modified DNA. The final result will be the relative ratio of *MGMT* methylation / beta-actin as compared with positive control coming with the DNA modification kit.

[name], (Project Coordinator NA) should be contacted before any shipment. Samples must arrive during business hours from Monday through Friday and shipped overnight to:

OncoMethylome Sciences SA

Attn: [name]

[name]

[name]

[name]

[contact]

Contact information for [name]:

[contact]

[contact]

Email: [contact]

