12.0 CRITERIA FOR THERAPEUTIC RESPONSE/OUTCOME ASSESSMENT

All patients will have their tumor measurements recorded at baseline and at the time of each MRI scan. Lesions must be measured in two dimensions. The dose of gadolinium must be held constant from scan to scan.

Because the first MRI obtained after radiotherapy often shows an increased pattern/area of enhancement of indeterminant significance this scan will not be used to assess response to therapy or to make a decision as to whether or not a patient remains on study. The first MRI after radiotherapy will be used as a new baseline scan for subsequent MRI assessments.

Complete response (CR) is the total disappearance of all measurable contrast enhancing tumor on two MRIs separated by at least 4 weeks. The patient must have no clinical neurologic deterioration or decrease in performance status. The patient must be off dexamethasone.

Partial response (PR) is at least a 50% reduction in the size of measurable contrast enhancement (the sum of the products of the greatest length and maximum width of all measurable lesions). No lesion may progress and no new lesions may appear. All PR should be confirmed by repeat MRI separated by at least 4 weeks. The dose of dexamethasone must be the same or lower than at baseline.

Stable disease (SD) exists when a patient fails to qualify for partial response or progressive disease.

IRB#: 05-079A(17)

Progressive disease (PD) is an increase of 25% or more in the size of any lesion or the appearance of a new site of tumor.

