14.2 Secondary endpoints include progression-free survival defined as the date of study entry to the first scan that demonstrates tumor progression (please note that the MRI after completion of radiotherapy will be used as the baseline scan for response assessment). Frequency of toxicity will be tabulated according to the NCI Common Toxicity Criteria (version 3.0). Methylation *MGMT* status will be assessed using real-time PCR. A Fishers exact test will be used to compare one year survival by MGMT status (methylated/unmethylated) in order to observe any trends similar to that from the retrospective EORTC/NCIC.

In addition, these regimens will be administered to forty patients with all other malignant glioma subtypes. Up to twenty patients in each arm will be accrued. Endpoints such as one-year survival probability, overall survival and progression-free survival will be computed in order to gain preliminary data for these other subtypes.

The minimum anticipated sample size would be 66 patients (23 in each cohort plus 20 patients with other malignant glioma subtypes.) If both cohorts accrue patients to the second stage then a total of 118 evaluable patients will be accrued (39 in each cohort + 40 patients with other malignant glioma subtypes). To ensure 118 evaluable patients, we will accrue 140 patients to guard against a 20% rate of ineligibility and patient drop out observed during an interim analysis. Patients who withdraw consent or are found to be ineligible can be replaced. The anticipated rate of accrual is 6 patients/month requiring 12-18 months to complete the accrual to the trial.

14.3 RANDOMIZATION:

Patients will be randomized to dose dense temozolomide or metronomic temozolomide. After eligibility is established and immediately after consent is obtained, patients will be registered in the Protocol Participant Registration (PPR) system and randomized using the Clinical Research Database (CRDB), by calling the MSKCC PPR registry at [contact] between the hours of 8:30 am and 5:30 pm, Monday - Friday. Randomization will be accomplished by the method of random permuted block, and patients will be stratified by KPS (<80 vs \geq 80).

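### Clinical progression bars a patient from maintenance under section 9.3, but it is neither progressive disease in section 12 nor a PFS event in section 14.2, and the scan that would record the event may never be scheduled.

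*Combined protocol and SAP*

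**What the plan says.** Five places in the protocol define or use progression.

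- **Section 9.3 (maintenance):** treatment starts in "patients who have had no clinical or radiographic evidence of tumor progression". The same section then says "Treatment will continue in 28 day cycles until tumor progression", without saying whether clinical progression counts at that stage.
- **Section 12 (response criteria):** "Progressive disease (PD) is an increase of 25% or more in the size of any lesion or the appearance of a new site of tumor". The residual category reads "Stable disease (SD) exists when a patient fails to qualify for partial response or progressive disease". Clinical status enters only the complete-response definition: "The patient must have no clinical neurologic deterioration or decrease in performance status". Partial response carries a dexamethasone condition but no neurologic one.
- **Section 10 (evaluations):** "patients with evidence of tumor progression as compared to the post radiotherapy MRI will be removed from the study". This applies to MRIs after every 2 adjuvant cycles and after every 2–3 maintenance cycles. No MRI is scheduled for a patient who finishes adjuvant therapy and does not enter maintenance.
- **Section 13 (removal):** patients leave the study for progressive disease, the term that section 12 defines.
- **Section 14.2 (secondary endpoints):** "progression-free survival defined as the date of study entry to the first scan that demonstrates tumor progression". Death is not named as an event, and no censoring rule for PFS is given.

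No section defines clinical progression or says how to score or date it.

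**The concern.** A treatment rule and an endpoint rule in the same protocol disagree on whether a patient has progressed. Section 12 recognises clinical decline when it denies a complete response but leaves it out of progressive disease, so a reader cannot assume that it is implied.

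PFS is the first secondary objective and is also to be computed for the other glioma subtypes, up to 20 patients per arm. Patients whom section 9.3 regards as progressed would be counted late or not at all, which lengthens the reported PFS. They are likely to have a poor prognosis, so censoring them would be informative. Two people applying the protocol could also score the same patient differently.

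**Working it through.** **Step 1: apply the rules to one patient.** Take a patient judged clinically progressed at the end of cycle 6, with no lesion grown by 25% and no new site.

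| Section | Result |
|---|---|
| 9.3 | Progressed; maintenance not started |
| 12 | Not progressive disease; usually stable, or partial response if the shrinkage and dexamethasone conditions are met |
| 13 | Not triggered, if the term is read as section 12 defines it |
| 10 | No further MRI scheduled, because later scans belong to maintenance |
| 14.2 | No PFS event unless an unscheduled scan shows progression |

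**Step 2: where scans can be lost.** During adjuvant therapy an MRI follows every 2 cycles (2 × 28 = 56 days), so a later scan can still record progression. During maintenance, MRIs continue every 2–3 cycles. The scheduled scan disappears at the gate after cycle 6.

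**Step 3: illustrative size.** The protocol states no figure for PFS that could be reproduced, so these inputs are assumptions: exponential PFS with median 7 months, and a share p of first progressions that are clinical-only, with p = 10% as the central case and a range of 5–20%. The arm size of 39 comes from section 14.1.

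- Hazard: λ = ln 2 / 7 = 0.0990 per month.
- True 12-month PFS: S(12) = exp(−0.0990 × 12) = 30.5%.
- Standard error: √(0.305 × 0.695 / 39) = 7.4 points.

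(a) *Recorded 3 months late.* Shift = p × [S(9) − S(12)], with S(9) = 41.0%. At p = 10%: 0.10 × 10.5 = 1.1 points. At 5% and 20%: 0.5 and 2.1 points.

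(b) *Censored only in the six adjuvant cycles.* These last 6 × 28 = 168 days, or 5.52 months, all assumed to fall before month 12. Shift = S(12) × [exp(p × λ × 5.52) − 1]. At p = 10%: 30.5 × (exp(0.0547) − 1) = 1.7 points. At 20%: 3.5 points.

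(c) *All clinical-only events censored, whenever they occur.* The hazard becomes λ(1 − p). At p = 10%: exp(−0.0990 × 0.9 × 12) = 34.3%, a shift of 3.8 points (3.9 by simulation of the same model), and the median becomes 7 / 0.9 = 7.8 months. At 5% and 20%: 1.9 and 8.2 points.

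Changing the assumed median to 5 or 9 months gives 3.4 or 3.8 points for case (c) at p = 10%.

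**The case against.** The strongest reply is that the rules serve different purposes. Section 9.3 decides who starts a treatment, while sections 12 and 14.2 score an endpoint. A treatment gate may be broader than an endpoint, and a scan-based PFS is defensible in an open-label trial because clinical judgement is more subjective. That stands as a defence of scan-based PFS in general. It does not answer the loss of scheduled scans: a scan-based endpoint needs scans, and section 10 provides none for the patients whom section 9.3 turns away.

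It is also fair that no decision rests on PFS. It has no threshold, hypothesis or between-arm test, and section 14.2 gives no PFS censoring rule, so censoring is itself an assumption. These points limit the importance without removing the inconsistency.

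A reader might infer more than the documents support:

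- **That the go/no-go decision is biased.** Sections 4.3 and 14.1 base it on one-year survival, which does not use progression.
- **That all clinical-only progressions are lost.** The MRI schedule before the gate and during maintenance makes case (c) an upper bound for a given share and median.
- **That PFS is biased against the published phase III regimen.** The background does not say how that trial defined progression.
- **That progressive disease means lesion growth only, or that the patient is always stable.** A new site also counts, and partial response is possible.

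**Conclusion.** The inconsistency is real and lies in the text. Followed as written, the plan overstates PFS in each arm relative to the concept of progression in section 9.3. The effect is confined to PFS, response category, and the coherence of the maintenance and removal rules.

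Its size cannot be derived from the documents, which give neither a median PFS nor a share of clinical-only progressions. Under the central assumptions, 1 to 2 points on 12-month PFS is the plausible illustration and just under 4 points the ceiling, about half a standard error for one arm of 39. Only the combination of a 20% share with every such event censored exceeds one standard error (8.2 against 7.4 points), and the MRI schedule makes that unlikely. This is a cheap improvement, not a threat to the trial's main conclusion.

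**What to change.** For endpoint scoring only, amend section 14.2 so that the PFS event date is the earliest of:

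1. documented clinical progression attributed to tumor;
2. the first scan meeting the section 12 criterion for progressive disease;
3. death from any cause.

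Report the scan-based version as a sensitivity analysis. Leave the section 12 term unchanged in this amendment, because section 13 uses it to remove patients and altering it would alter clinical management.

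Separately, sections 9.3, 10, 12 and 13 must be reconciled on whether clinical progression counts for treatment and removal. This review does not say which rule is right.

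The cost is protocol wording and one extra analysis. Exams are already monthly during adjuvant therapy and roughly monthly for the first 6 months of maintenance. The downside is that clinical progression is more subjective in an open-label trial, which the scan-based analysis would expose. The reported PFS would also be slightly less favourable.
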